When inflated, the cuff constricts the urethra and blocks the passage of any urine. When deflated, the cuff reduces pressure on the urethra and allows for the free passage of urine.

[figure not shown]

Figure 5 AUS with Foley catheter

A foley catheter is also inserted during surgery, which is removed prior to discharge from the hospital. The artificial sphincter cuff is not inflated immediately after surgery, in order to allow the tissues to heal.

Significance:

Post-prostatectomy urinary incontinence is a troubling complication following treatment (radical prostatectomy, radiation therapy, or brachytherapy) for prostate cancer, or in rare instances the treatment of benign prostatic hypertrophy, and significantly decreases quality of life in affected patients. An artificial urinary sphincter has been found to significantly improve quality of life in these patients. Providing data which demonstrates the safety and feasibility to activate an artificial urinary sphincter 3 weeks after surgery as opposed to 4-6 weeks will allow men to regain their continence earlier, therefore improve their quality of life.

Methods

Study Design:

The design will be a single institute prospective study with patients undergoing artificial urinary sphincter placement by the operating surgeon, [name] at Charleston Area Medical Center in Charleston, WV. All patients following informed consent that meet the inclusion criteria are eligible to participate in the study.

Sample:

All male patients with moderate to severe urinary incontinence who have been treated for prostate cancer (radical prostatectomy, External Beam Radiation therapy or brachytherapy, or Incontinence related to trans urethral resection of the prostate (TURP) or simple prostatectomy undergoing artificial urinary sphincter placement at Charleston Area Medical Center by [name], D.O. will be offered the chance to participate in this study. This is a pilot study and thus no power analysis to calculate necessary sample size is conducted to determine a number that would yield sufficient power. We will aim to enroll 25 patients, which we anticipate to be accrued within 3 years from the start of the study. We will have 1 study group: those who are activated at 3 weeks post implantation.

Inclusion Criteria:

All patients undergoing artificial urinary sphincter (AUS) placement by a single surgeon, [name].

Exclusion Criteria:

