Any patient who has previously undergone artificial urinary sphincter placement and presents for revision or additional cuff placement.

Any patient who is undergoing combined artificial urinary sphincter and inflatable penile prosthesis placement.

Any patient who is a poor candidate for early activation due to poor condition at presentation or signs of infection.

Procedures and Protocol:

There isn't a comparison group for this study; therefore all patients agreeing to participate will have the urinary sphincter activated 3 weeks after surgery. If there are patients that later choose not to have early activation or are found to be poor candidates for three week activation based upon their post op

exam, we will proceed with activation at a 4-6 week time period. While there is no comparison group in the study, patient satisfaction and adverse events for study patients will be compared to historical literature.

Currently patients are not routinely seen for a 3 week follow up appointment, so approximately \$3000 will be requested from Research appropriations to cover the costs of this study. All other costs are standard of care, so patient will be responsible for those costs whether they agree to enroll in the study or not. The money from the CAMC Research Appropriations will be used to cover all the clinical fees for the 3 week visit to activate the AUS.

Pre-procedure:

- 1. All eligible patients will be informed about the study at their regularly scheduled pre-operative office visit. If the patient agrees to participate, they will be consented with the consent form as written. A note is made in the progress note of the patient's chart detailing the consent.
- Original signed consent will be kept and stored in the consent binder at [name] office and one copy of the consent will be placed in the medical record and another will be given to the participant.
- 3. Patient will complete an SF-8 quality of life survey and Incontinence Impact Questionnaire (Appendix A).

Intraoperative procedures:

1. Once consented, the patient will undergo the procedure without any changes to our normal routine. The patient's device will be deactivated at the conclusion of the procedure.

Post-procedure:

- 1. The patient will be discharged post-operatively (same day) and follow-up will be arranged in 3 weeks to activate the device.

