- 2. Study patients have a follow up office visit at 3 weeks (up to 3 weeks and 3 days after the procedure) which includes a post-operative evaluation of their incisions, degree of bruising, tissue induration, tenderness and accessibility of the pump. If these factors are acceptable and pump mechanics are normal, the artificial sphincter will be activated and the patient will be educated on its proper use.
- 3. Additional follow up will include the regular 6 week visit, a visit at 3 months, and then every 6 months for a total of 1 year unless issues arise that necessitates deviation. At each visit, patients will complete the Incontinence Impact Questionnaire and the SF-8 quality of life survey.

Study Chart:

INFORMATION	PRE-	Intra-	POST-Treatment	POST-	POST-	POST-	POST-Operative
	Treat	operative	3 weeks	OperativeTrea	Operative	Operative	Treatment 1 year
	ment	Treatment	(up to 3 weeks and	tment	Treatment 3	Treatment	(+ 1 month)
			3 days after	6 weeks	months	Six months	
			procedure)	(+ 1 week)	(+ 2 weeks)	(+ 3 weeks)	
Inform Subject	Х						
Consent Subject	Х						
Note in Record	Х						
Office visit	Х		Х	X	Х	Х	Х
SF-8 survey administered	Х			Х	Х	Х	Х
Incontinence Impact Questionnaire	Х		Х	Х	х	Х	Х
Procedure conducted		Х					
Data Collection	Х	X	Х	Х	Х	Х	Х

Data Collection and Management:

The SF-8 is a quality of life instrument related to health functioning that provides an eight question brief assessment of physical and mental health⁶. It has been found to have adequate reliability and validity in prior studies for quality of patient life and it incorporates a manual for easy interpretation.⁷. The Incontinence Impact Questionnaire short form was adapted from a survey that was developed for women with stress incontinence. This questionnaire has been validated for use in men after radical prostatectomies and consists of 7 items in which measures the effect of Urinary Incontinence on quality of life⁸.

Following surgery, patient characteristics and operative details will be recorded. These will include:

- Medical Record Number
- Patient name
- Age
- BMI
- Operative time
- Artificial sphincter cuff size
- Pressure-regulating balloon size
- Intra-operative complications (urethral injury, bleeding)
- Reason for AUS placement (Post-prostatectomy, Radiation therapy for prostate cancer, or Incontinence related to TURP)
- Finish date of prostate cancer treatment or TURP
- Preoperative daily pad usage
- Pre-surgery SF-8 survey

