- History of medication
- Date device is activated
- Comorbidities
- ECOG Score

- ASA Score
- Tobacco Use
- Diabetes

When the study patient follows up at 3 weeks postoperatively, we will assess for immediate postoperative complications:

- Post-operative urinary retention Y/N
- Bleeding Y/N
- Presence/concern for infection Y/N
- Presence/concern for urethral erosion Y/N

When any patient follows up at 6 weeks, 6 months, and 12 months postoperatively, we will assess:

- Postoperative daily pad usage
- Perceived improvement in incontinence (scale 1 (none) 10 (very satisfied))
- Presence/concern for infection Y/N
- Presence/concern for urethral erosion Y/N
- Post-surgery SF-8 surveys (6 weeks, 3 months, 6 months)

Statistical Analysis:

The Center of Health Service and Outcomes Research will conduct the data analysis. For this exploratory study, selection of appropriate statistical measure will be determined by CAMC Center for Health Education and Research Institute. Specific tests will be determined by whether the data is continuous or categorical. Descriptive statistics will be used as appropriate and comparisons will be done using student's T-test and chi-square test. In addition univariate and multivariate multiple logistic regressions will be used to determine which variables predict patient's outcomes. All comparisons will be done at 95% of level of significance.

I. Human Subjects

Study population: All patients undergoing artificial urinary sphincter (AUS) placement by a single surgeon, [name] at Charleston Area Medical Center.

Recruitment methods: All patients, following informed consent, that meet the inclusion criteria are eligible to participate in the study. Patients will be consented by the principal investigator only at time of usual surgical informed consent using the attached consent form. Consent will be obtained prior to the surgical procedure.

Benefits: Early activation of the artificial urinary sphincter will allow the patient to regain continence earlier.

Risks and discomforts: The principle risks of participation in this study will be the standard risks of the operation.

Less often, there are risks of bleeding, infection, urinary tract injury, device erosion, wasting away of muscle mass in the urinary tract, or loss of bladder control.

Occasionally, there are risks of persistent loss of bladder control or mechanical failure of device.

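### Adverse events are compared with the literature without a split at activation, so findings already present at the 3-week examination can be mixed into the early-activation result

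*Combined protocol and SAP*

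**What the plan says.** The Aim of the study is to learn whether activation at 3 weeks raises the risk of postoperative complications; the hypothesis is that it does not. There is one arm: "We will have 1 study group: those who are activated at 3 weeks post implantation".

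Under Intraoperative procedures, the device is left deactivated when surgery ends. Under Post-procedure, item 2, the 3-week visit begins with an examination, and then: "If these factors are acceptable and pump mechanics are normal, the artificial sphincter will be activated". Procedures and Protocol describes this visit as outside usual care: "Currently patients are not routinely seen for a 3 week follow up appointment". The same section sends patients who decline, or who prove unsuitable on examination, to activation at 4-6 weeks.

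Data Collection and Management gives the first complication list: "When the study patient follows up at 3 weeks postoperatively, we will assess for immediate postoperative complications". Its four yes/no items are retention, bleeding, infection and erosion. The later list, for 6 weeks, 6 months and 12 months, keeps infection and erosion only. The activation date is recorded.

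The safety comparison is one clause in Procedures and Protocol: "patient satisfaction and adverse events for study patients will be compared to historical literature". Neither that section nor Statistical Analysis gives an event window, an event definition, a reference rate or a split at activation.

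**The concern.** The study asks what happens after the device is switched on at 3 weeks. A complication found before that moment reflects the operation, not the timing of activation. The 3-week visit is also an added opportunity to record events: a transient sign, or a mere concern about infection, can be noted when this centre's usual schedule has no routine visit.

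If such findings are pooled with later ones, the reader cannot tell which events bear on early activation. The planned lists sharpen the problem. The Background names retention as the most common complication, yet retention and bleeding are listed only at the visit where activation takes place. A finding that led to deferred activation could also be counted against early activation, because the deferred patient remains a study patient.

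**Working it through.** **Plan's own figure.** The only number is the enrolment target: "We will aim to enroll 25 patients, which we anticipate to be accrued within 3 years from the start of the study". It has no calculation behind it ("This is a pilot study and thus no power analysis to calculate necessary sample size is conducted"), so there is nothing to reproduce.

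**Planned complication items against activation, for a patient activated at 3 weeks.**

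| Visit | Retention | Bleeding | Infection | Erosion | Position |
|---|---|---|---|---|---|
| 3 weeks | yes | yes | yes | yes | visit at which the device is activated |
| 6 weeks | no | no | yes | yes | after |
| 6 months | no | no | yes | yes | after |
| 12 months | no | no | yes | yes | after |

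Infection and erosion can be compared before and after activation. Retention and bleeding have no planned assessment at any later visit. For a patient deferred to 4-6 weeks, the 6-week findings may also precede activation. The split must therefore follow the activation date, not the visit label.

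**Weight of one patient.** With n = 25, one patient whose only event precedes activation adds 1/25 = 4 percentage points to the crude rate.

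**Illustration with exact (Clopper-Pearson) 95% intervals.** The lower limit is the 0.025 quantile of Beta(x, n-x+1), and the upper limit is the 0.975 quantile of Beta(x+1, n-x).

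- Two patients with a pre-activation event, none later, pooled: 2/25 = 8%, CI 1.0-26.0%.
- After activation, if all 25 are activated at 3 weeks: 0/25 = 0%, upper limit 1 - 0.025^(1/25) = 13.7%.
- If those two are deferred, among the 23 activated at 3 weeks: 0/23 = 0%, upper limit 1 - 0.025^(1/23) = 14.8%.

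**How likely is at least one such patient?** The probability is 1 - (1-p)^25. The documents give no complication rate, so p is assumed.

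| Assumed p before activation | Chance of at least one in 25 |
|---|---|
| 2% | 40% |
| 5% | 72% |
| 10% | 93% |
| 20% | 99.6% |

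**What extra detection could do, if the literature had none.** The plan's criterion is "All comparisons will be done at 95% of level of significance", with sidedness not given. I assume a one-sided exact binomial test at 0.025, no effect of early activation, and 5 or 10 points of extra detected events. The entries are the chance of declaring an increase.

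| Assumed literature rate | Critical count of 25 | No extra detection | +5 points | +10 points |
|---|---|---|---|---|
| 5% | 5 | 0.7% | 9.8% | 31.8% |
| 10% | 7 | 0.95% | 7.0% | 22.0% |

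This last table is conditional. It says nothing about whether the chosen literature lacks the same detection.

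**The case against.** The best case against the point is that pooling is inferred. No sentence says that the 3-week findings enter the comparison or that one total will be reported. The 3-week list has its own label, the activation date is recorded, and the analysis is described as exploratory. This stands, and it makes the point a gap in the specification rather than a stated error. The comparison clause is nonetheless unrestricted, and nothing excludes or separates those events.

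A reader might go further and infer that the extra visit inflates the study's rate against the literature. The documents do not support that. The absence of a routine 3-week visit describes this centre; the comparator is published series whose visit schedules and counting windows are not given. If they count from implantation, a total from surgery is like-for-like, and dropping the 3-week events would bias the comparison the other way. Any extra detection would also make the hypothesis of no rise harder to support, which is cautious for a safety claim.

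A reader might also count form items (4 at 3 weeks out of 4 + 2 × 3 = 10) and conclude that 40% of events precede activation. Form cells are not events, so that share has no meaning as an event rate.

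Nor is it certain that nothing recorded at 3 weeks could follow activation. The text does not say whether the yes/no list is completed before or after the device is switched on at that visit, and the Background mentions past patients who activated the device themselves soon after discharge. The point is therefore limited to complications already present at the examination, and to activation under the protocol.

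Finally, resting the early-activation statement on the post-activation period alone, with the present forms, would leave out retention and bleeding altogether. That is correct, and the fix has to deal with it.

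**Conclusion.** The point holds in a limited form. As written, the plan cannot separate events that could be due to early activation from events that precede it, although it collects the date needed to do so. For retention and bleeding, the planned lists cannot show an effect of early activation at all. Infection and erosion are assessed on both sides of activation, so that part of the comparison can be recovered.

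The size is 4 percentage points per affected patient, on the assumption that 25 are enrolled. The 8% against 0% contrast is hypothetical and assumes that both patients with early findings were still activated at 3 weeks. All complication rates and detection increments used above are assumptions. The direction and size of any distortion against the literature cannot be determined from the documents. In a 25-patient pilot this is a correctable reporting and data-collection gap, worth closing because it concerns the study's own safety question.

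**What to change.** In Statistical Analysis, specify:

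1. Adverse events tabulated in two periods, surgery to activation and after activation, divided at each patient's recorded activation date.
2. The cumulative rate from surgery shown beside literature with a matching window and definitions, with events found only at the 3-week visit flagged.
3. The post-activation table used for attribution to early activation, with patients deferred to 4-6 weeks shown separately.

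In Data Collection and Management, add the retention and bleeding yes/no items to the existing post-activation visit forms so that the second table covers them. State also whether the 3-week list is completed before the device is switched on.

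The cost is a little more tabulation, two extra form items and a line of form instruction; no new visit is needed. The numbers in each period will be small and should be presented with exact intervals.

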Early Activation of Artificial Urinary Sphincter: A Pilot study

Abstract:

Urinary incontinence or loss of bladder control is a troublesome issue for all affected patients. The causes of urinary incontinence and its treatment options vary widely. A commonly encountered reason for urinary incontinence in men is related to treatment for prostate cancer. These treatment options can range from surgical removal of the prostate, external beam radiation therapy, and/or brachytherapy, the insertion of radioactive implants directly into the tissue. Mild cases of incontinence are responsive to more conservative measures, but moderate to severe cases often require placement of an artificial urinary sphincter. Typically, these devices are left deactivated for a period of 4- 6 weeks following implantation to allow swelling to subside before use. We hypothesize that the device could be activated within an earlier timeframe without increasing the risk of complications. No studies to date have evaluated this; therefore we plan to conduct a prospective study in which we will activate the device 3 weeks after placement and monitor for complications.

Aim of the study:

To assess the safety and feasibility of early activation of an artificial urinary sphincter and assess whether or not this increases the risk of postoperative complications. We hypothesize that a period of 3 weeks should allow adequate time for the resolution of urethral and scrotal swelling following artificial urinary sphincter placement, and that activation of the device at that time, as opposed to traditional 4-6 weeks post-operatively, will lead to improved patient satisfaction with no increase in postoperative complications.

Background:

Urinary incontinence is one of the most common complications following surgical treatment of prostate cancer via radical prostatectomy. All patients will have this to some degree in the initial post-operative period, but it typically resolves over time as the newly created urethrovesical anastomosis heals. Wolin et. al reported a 59% rate of urinary incontinence at 6 weeks post-prostatectomy among studied patients¹. For the unfortunate patients who have persistent incontinence requiring the use of multiple pads per day in the absence of a bladder neck contracture or stricture, an artificial urinary sphincter (AUS) may be the best option to regain continence.

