The AUS was first introduced into practice in 1972 at the Baylor College of Medicine. Since that time, it has been found to effectively improve the quality of life of patients with post-prostatectomy urinary incontinence. In a recent analysis, 79% of patients report being satisfied and using no more than one pad per day². The device has undergone numerous revisions since its introduction and the current model, the American Medical Systems (AMS) 800, is widely implanted throughout the U.S. and worldwide. Several studies have been performed validating the AUS as a surgical treatment of post prostatectomy incontinence. There have been varying degrees of success documented in the literature secondary to the different definitions of success used, however, using the definition of zero to 1 pad per day, success rates have varied between 60% and 90% in modern series(3). The most common

complication is urinary retention, which can be managed with a urethral catheter. Less common complications include infection, device malfunction, and urethral erosion³.

The device (see figure 1) is placed in the operating room under general anesthesia. The device consists of a urethral cuff, pressure regulating balloon, and an activation pump and once activated, the urethral cuff will be closed at rest. The patient will squeeze the scrotal pump to open the cuff in order to void once the need arises. Patients are typically discharged the same day without a Foley catheter, unless unable to void in the recovery room. The device is typically left in the de-activated position to allow reductions in urethral edema and scrotal edema before the patient is allowed to manipulate the device. The device is routinely activated at 4-6 weeks post-operatively⁴. A literature review did not reveal any papers or guidelines that show that this period of de-activation of 4-6 weeks is actually required, though Baylor College of Medicine reports current practice of only waiting 4 weeks until activation⁵. There have not been any studies conducted indicating any negative consequences of activating the device early and there have been two or three patients at CAMC who have activated their device a few days post discharge from the hospital, against our advice.. These patients did not report any adverse events with early activation.

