There are possible complications associated with AUS placement. Complications that occur less often include bleeding, infection, urinary tract injury, device erosion, wasting away of muscle mass in the urinary tract known as sub cuff atrophy, or loss of bladder control. Complications that may occur occasionally include persistent loss of bladder control or Mechanical Failure of device. These are risks associated with any AUS procedure and patients participating in this study will not be at higher risk for these than those who chose not to participate.

[figure not shown]

Figure 1. Implanted Artificial Urinary Sphincter (AUS) demonstrating attachments of the cuff to the pressure regulating balloon and intra-scrotal pump4.

Reconstructive Urology, Urology and Urodynamics

[figure not shown]
[figure not shown]

Figure 2 Artificial Urinary Sphincter (AUS)

An artificial urinary sphincter is used to treat stress incontinence in men, which is caused by urethral dysfunction (usually after prostate surgery). Additionally, this procedure is performed in both men and women with sphincter dysfunctions related to spinal-cord injury or multiple sclerosis. Before resorting to this treatment, most experts advise using medication and bladder-retraining therapy. Alternatives to this procedure include the pubovaginal sling in women, or the periurethral injection of collagen in both men and women.

adam.com

Figure 3 Implanted AUS

An artificial sphincter consists of: a cuff that fits around the bladder neck a pressure regulating balloon a pump that inflates the cuff to treat urinary incontinence, a cuff is placed around the bladder neck so that when it is inflated, the urethra closes tightly. The pressure-regulating balloon is placed under the tissues of the lower abdomen. The balloon is then filled with liquid (occasionally, an iodine-based solution is used so that it will be visualized when x-ray procedures are performed). The control-pump mechanism is placed in the labia for women, and in the scrotum for men. To use the sphincter, compress (squeeze) the pump so that fluid is diverted from the urethral cuff to the balloon. This action enables the sphincter to relax, which in turn, enables you to urinate. The cuff re-inflates on its own in three to five minutes.

[figure not shown]

Figure 4 Inflation of AUS

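### After activation the protocol's assessment list has only infection and erosion as complications, so device malfunction, sub-cuff atrophy, retention and bleeding have no planned systematic capture

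*Combined protocol and SAP*

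**What the plan says.** **Purpose.** Under Aim of the study, the trial is to examine safety and feasibility and to "assess whether or not this increases the risk of postoperative complications". The stated hypothesis is that complications will not increase. Procedures and Protocol says there is no concurrent comparison group, and that "patient satisfaction and adverse events for study patients will be compared to historical literature".

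**Complications the protocol names.** Background ranks urinary retention as the commonest, then says "Less common complications include infection, device malfunction, and urethral erosion". Further on, Background includes among the risks "wasting away of muscle mass in the urinary tract known as sub cuff atrophy", and adds: "Complications that may occur occasionally include persistent loss of bladder control or Mechanical Failure of device". Risks and discomforts, under Human Subjects, repeats mechanical failure and describes the same muscle wasting.

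**Why the device is normally left off.** Background gives the reason as "to allow reductions in urethral edema and scrotal edema before the patient is allowed to manipulate the device".

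**What is to be recorded.** Data Collection and Management has two lists. The 3-week list has four yes/no items: retention, bleeding, infection and erosion. The later list is introduced by "When any patient follows up at 6 weeks, 6 months, and 12 months postoperatively, we will assess". It contains daily pad use, perceived improvement on a 1 to 10 scale, "Presence/concern for infection Y/N", the matching item for urethral erosion, and the SF-8.

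**Visits.** Post-procedure and the Study Chart schedule visits at 6 weeks, 3 months, 6 months and 1 year, with the IIQ-7 at each. Incisions, bruising, induration, tenderness, access to the pump and pump mechanics are examined at 3 weeks to decide whether to activate. No later visit repeats that examination.

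**The concern.** A study of whether early activation adds complications needs to record, after activation, the complications it recognises. Here the protocol's inventory of risks and its post-activation assessment list do not match. Two device-related complications that it names are never assessed, and two others are assessed only before the man has lived with an active cuff.

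The gap also lies close to the mechanism under test. The protocol ties the usual delay to swelling that should settle before the pump is handled, so earlier activation means earlier handling. Yet the pump and scrotum are examined only at the visit where activation is decided, which comes before the exposure and cannot show its effect.

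The direction matters. Leaving out event types cannot raise the number of men with a complication and may lower it, and a lower count favours the hypothesis of no increase. There is no control group in which the same omission would occur, and the planned comparator is literature that may count a different set of events.

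**Working it through.** The protocol gives no event rate, margin or power calculation to reproduce; 25 is a recruitment aim. The check sets the named complications against the assessment lists.

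**Step 1. Coverage.**

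| Complication | Where named | 3-week list | 6-week, 6- and 12-month list | 3-month visit |
|---|---|---|---|---|
| Infection | Background; Risks and discomforts | yes | yes | no item |
| Erosion | Background; Risks and discomforts | yes | yes | no item |
| Urinary retention | Background (commonest) | yes | no | no item |
| Bleeding | Background; Risks and discomforts | yes | no | no item |
| Malfunction or mechanical failure | Background (twice); Risks and discomforts | no | no | no item |
| Sub-cuff atrophy | Background; Risks and discomforts (as muscle wasting) | no | no | no item |
| Urinary tract injury | Background; Risks and discomforts | no (urethral injury is an intra-operative item) | no | no item |
| Loss of bladder control | Background; Risks and discomforts | no | indirectly, by pad use | no item |

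**Step 2. Count over the scheduled post-activation visits (6 weeks, 3 months, 6 months, 12 months).** Infection and erosion are listed at 3 of 4. Retention, bleeding, malfunction and sub-cuff atrophy are listed at 0 of 4. The later list mentions 3 months only beside the SF-8.

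**Step 3. Timing of the 3-week items.** They belong to the visit at which the device is switched on, if the examination allows it. Answers about retention and bleeding there describe the period with the cuff off.

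**Step 4. Could other items stand in?** Pad use, perceived improvement and the IIQ-7 may worsen if a device fails. They cannot separate malfunction from atrophy or from persistent incontinence, and they do not record surgery. A man revised between visits and dry at the next one would show nothing on these measures. Revision appears only in Exclusion Criteria; removal of a device appears nowhere.

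**Step 5. Size.**
- One event in one man out of 25: 1/25 = 4 percentage points.
- If no event of a listed type is seen in 25 men, the exact one-sided 95% upper limit is 1 − 0.05^(1/25) = 11.3%. For a type that is not collected, no such limit can be given.
- The share of events missed would be u/(c + u), where c is the rate of listed events and u the rate of unlisted events. The documents give neither, so this is not evaluated.

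**The case against.** The strongest reply is that the later list is not said to be exhaustive. The Abstract promises to monitor for complications; Procedures and Protocol speaks of adverse events in general; the Study Chart has a data-collection row at every visit; Confidentiality provides for review of medical records; and visits may depart from schedule if problems arise. A surgeon who re-operates on a study patient will know of it. The case report forms are not in the documents (Appendix A holds only the SF-8 and the IIQ-7), so they may carry more fields than the protocol describes. And this is a pilot.

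Part of this stands. Four stronger readings that a reader might infer are not supported:

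- *That these events will go uncounted, or that a man with a failed pump would be reported as free of complications.* Some events could surface by the routes above. What can be shown is that none of those routes defines an item, an adverse-event definition or a reporting period.
- *That a particular share of complications will be missed.* That needs rates the documents do not contain.
- *That the literature comparison is already unlike with unlike.* No comparator series or endpoint is named, so this is a risk and not a demonstrated fact.
- *That pump-site problems and revision or removal are complications the protocol recognises.* It does not name them as such. They are reasonable additions; malfunction, atrophy and retention carry the point.

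The pilot label does not remove the point. Safety is the stated aim, and no sample-size argument is made here.

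**Conclusion.** The point holds for the protocol's assessment list. After activation it has two complication items, infection and erosion, at 3 of 4 scheduled visits. Malfunction and sub-cuff atrophy are on no list, retention and bleeding are listed only for the time before activation, and the 3-month visit has no complication items. There is no planned systematic capture of these events, and the count to be compared with the literature risks being biased low, toward the hypothesis of no increase.

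The size is 4 percentage points per missed event, if 25 men are enrolled and followed and each missed event falls in a different man who has no other recorded complication. The conclusion assumes that data collection follows the written list; fuller case report forms would reduce the problem, but the protocol would still need to say so. The change should be made, because the omission touches the main aim and is cheap to correct.

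**What to change.** Replace the later list with one predefined complication list used at 6 weeks, 3 months, 6 months and 12 months. Each item is yes/no with date of onset:

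- infection
- urethral erosion
- urinary retention
- bleeding
- device malfunction, with the component
- sub-cuff atrophy
- pump-site problems or inability to operate the pump
- any device re-operation (revision, removal or replacement), with the reason
- an open adverse-event item

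Report each type separately, and report re-operation for any cause by 12 months. Compare with the literature only for events that the chosen comparator also counts, and name those events in the plan.

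The cost is one protocol and data-form amendment and a few extra fields at visits already scheduled. The reported complication rate may be less favourable.
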